9.5 Prior and Concomitant Medications

Information regarding prior and concomitant medications, including CF medications, other medications, and herbal and naturopathic remedies, will be collected from each subject's source documentation for medications taken within 56 days before the Screening Visit through completion of study participation, as defined in Section 9.1.6.

For subjects who are screened but are not subsequently enrolled, details of prior medication will be documented only in the subject's source documents.

- Subjects should remain on a stable treatment regimen for their CF from 28 days before the Day 1 Visit through completion of study participation. Stable treatment regimen is defined as the current treatment regimen for CF that subjects have been following for at least 28 days before the Day 1 Visit. Subjects should not initiate long-term treatment with new medication from 28 days before the Day 1 Visit through completion of study participation. Guidelines for stable treatment regimens for CF are as follows:
 - o Subjects who are taking inhaled tobramycin or other chronically inhaled antibiotics should remain on that regimen throughout the study.
 - o Subjects who cycle onto and off of an inhaled antibiotic should continue on their prior schedule. The timing of the first dose of study drug on the Day 1 Visit should be synchronized as closely as possible (e.g., not more than ± 3 days) to the first day in the cycle onto the inhaled antibiotic.
 - o Subjects who alternate between 2 different inhaled antibiotics should remain on the same cycling schedule during the study. The timing of the first dose of study drug on the Day 1 Visit should be synchronized as closely as possible (e.g., not more than ± 3 days) to the first day in the cycle onto 1 of the inhaled antibiotics.
- Subjects may receive doses of prednisone or prednisolone of up to 10 mg/day chronically, or up to 60 mg daily for up to 5 days.
- ELX may inhibit OATP1B1 and OATP1B3, which may increase the exposure of medicinal products that are substrates for these transporters. Substrates such as statins, glyburide, nateglinide, and repaglinide should be used with caution.
- IVA is a weak inhibitor of P-glycoprotein (P-gp). Administration of IVA may increase systemic exposure of medicinal products that are sensitive substrates of P-gp, which may increase or prolong their therapeutic effect and adverse reactions. Digoxin or other substrates of P-gp with a narrow therapeutic index, such as cyclosporine, everolimus, sirolimus, and tacrolimus, should be used with caution and appropriate monitoring.
- IVA may inhibit CYP2C9; therefore, during coadministration with warfarin, additional monitoring of the international normalized ratio is recommended. Other medicinal products that are CYP2C9 substrates for which exposure may be increased include glimepiride and glipizide; these should be used with caution.
- Information about bronchodilator use during the study will be collected and documented. Subjects who are using a bronchodilator should have their MBW assessments performed according to the guidelines provided in Section [11.4.2](#).

9.6 Administration

9.6.1 Dosing

Study drug will be orally administered with the approved foods and liquids listed in the Study Manual (e.g., apple sauce). The doses to be administered are shown in [Table 9-1](#).

Study drug should be administered within approximately 30 minutes of the start of a fat-containing meal or snack, such as a standard “CF” meal or snack or a standard meal according to the following guidelines:

1. On days of scheduled visits, the morning dose of study drug will be administered at the site after predose assessments have been completed.
2. All doses of study drug (morning and evening, as applicable) should be administered at approximately every 12 hours (± 1 hour for **Part A** and ± 2 hours for **Part B**) on each dosing occasion. For example, if the morning doses of study drug are administered at 08:00 hour on Day 1, all subsequent morning doses should be administered between 07:00 hour and 09:00 hour for **Part A**, and between 06:00 hour and 10:00 hour for **Part B**.
3. At the Day 1 Visit, all subjects will be observed for 4 hours after the morning dose of the study drug.
4. The date, amount taken, and time of study drug administration including whether food was taken with each dose, will be recorded for 2 days before PK sample collection and on the days of PK sample collection.
5. For visits after the Day 1 Visit, subjects will be instructed to bring all used and unused study drug to the site; study drug will be dispensed at each visit, as appropriate.
6. **Part A:** At the Day 15 Visit, only the morning dose of study drug will be administered.
Part B: At the Week 24 Visit, the morning dose of study drug will NOT be administered. The last dose of study drug will be the evening dose administered the day before the Week 24 Visit.

9.6.2 Missed Doses

If 6 hours or less have passed since the missed morning or evening dose, the subject should take the missed dose as soon as possible and continue on the original schedule.

Morning dose: If more than 6 hours have passed since the missed **morning** dose, the subject should take the missed dose as soon as possible and should not take the evening dose.

Evening dose: If more than 6 hours have passed since the missed **evening** dose, the subject should not take the missed dose. The next scheduled morning dose should be taken at the usual time.

Morning and evening doses should not be taken at the same time.

9.7 Dose Modification for Toxicity

No dose modifications for toxicity are allowed. If any unacceptable toxicity arises, individual subjects will discontinue dosing (Section 9.1.4).

9.8 Study Drug Interruption and Stopping Rules

In subjects who have interrupted study drug for >72 hours for any reason, the investigator should resume study drug only after a thorough investigation of the cause for interruption. The investigator will evaluate the subject’s clinical stability and should consider resumption of study drug only after the subject is clinically stable and there is no comorbidity or condition that, in the opinion of the investigator, might confound the results of the study or pose an additional risk in administering study drug to the subject.

The medical monitor should be notified of an interruption of study drug that lasts >72 hours for any reason and of the resumption of study drug after such interruption. In subjects for whom study drug was previously interrupted, the medical monitor should be notified of any plan to discontinue study drug, before the discontinuation has occurred, if possible.

9.8.1 Liver Function Tests

The central laboratory will notify the medical monitor of ALT or AST $>3 \times$ ULN and total bilirubin $>2 \times$ ULN that are derived from centrally submitted samples.

Subjects with new treatment-emergent ALT or AST elevations of $>3 \times$ ULN, with or without total bilirubin $>2 \times$ ULN, must be followed closely, including confirmatory testing performed by the central laboratory within 48 to 72 hours of the initial finding and subsequent close monitoring of ALT, AST, and bilirubin levels, as clinically indicated.

If a subject cannot return to the site for confirmatory testing, a local laboratory may be used. Local laboratory results must be reported immediately to the medical monitor, and the subject must have the tests repeated and sent to the central laboratory as soon as possible (ideally within 48 to 72 hours).

Study drug administration **must be interrupted** immediately (prior to confirmatory testing) if any of the following criteria are met:

- ALT or AST $>8 \times$ ULN
- ALT or AST $>5 \times$ ULN for more than 2 weeks
- ALT or AST $>3 \times$ ULN, in association with total bilirubin $>2 \times$ ULN and/or clinical jaundice

A thorough investigation of potential causes should be conducted, and the subject should be followed closely for clinical progression.

Study drug administration **must be discontinued** if the following criteria are met:

- Subsequent ALT or AST values confirm the initial elevation that satisfied the interruption rule (above), and no convincing alternative etiology (e.g., acetaminophen use, viral hepatitis, alcohol ingestion) is identified, regardless of whether transaminase levels have improved

All subjects in whom treatment is discontinued for elevated transaminases (and bilirubin, as applicable) should have these levels monitored closely until levels normalize or return to baseline.

If an alternative, reversible cause of transaminase elevation with or without increased bilirubin or clinical jaundice has been identified, study drug administration may be resumed once transaminases return to baseline or are $\leq 2 \times$ ULN, whichever is higher. Regardless of the duration of interruption, the medical monitor should be notified prior to resumption of study drug. Upon resumption of study drug, transaminases and bilirubin should be assessed weekly for 4 weeks. If a protocol-defined transaminase elevation interruption threshold recurs within 4 weeks of rechallenge with the study drug (with confirmation of the initial elevation by repeat testing within 48 to 72 hours), then the study drug must be permanently discontinued, regardless of the presumed etiology.

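### The liver restart rule covers children with raised bilirubin or jaundice, but its only stated recovery condition is for transaminases

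*Protocol*

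**What the plan says.** Protocol Section 9.8.1 lists three triggers for immediate interruption. The third combines ALT or AST above 3× ULN "in association with total bilirubin" above 2× ULN and/or clinical jaundice.

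The restart sentence applies when another, reversible cause of "transaminase elevation with or without increased bilirubin or clinical jaundice has been identified". In that case "study drug administration may be resumed once transaminases return to baseline" or are no more than 2× ULN, whichever is higher. Two further requirements accompany it: "the medical monitor should be notified prior to resumption of study drug", and after restart "transaminases and bilirubin should be assessed weekly for 4 weeks".

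Before restart, Section 9.8.1 asks for an investigation of causes, close clinical follow-up, and "subsequent close monitoring of ALT, AST, and bilirubin levels, as clinically indicated". The parent Section 9.8 adds a general condition for interruptions longer than 72 hours, whatever the reason. The cause must be investigated, and the investigator "should consider resumption of study drug only after the subject is clinically stable" and has no condition that might confound the results or add risk.

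The SAP summarises bilirubin against thresholds (Appendix D) but contains no restart rule.

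**The concern.** The restart sentence names raised bilirubin and jaundice when it defines which cases it covers, then drops both when it says what must have recovered. In the third trigger, bilirubin or jaundice is part of what forces the interruption. One would expect the same sign to appear in the condition for going back on drug.

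At stake is consistency of a written safety rule in children aged 2 through 5 years, in a study part whose primary objective is safety. Two sites applying Section 9.8.1 to the same child could reach different decisions, because transaminases have a number and bilirubin has none. Post-restart testing would show a persisting bilirubin elevation, but only after re-exposure.

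**Working it through.** There is no plan figure to reproduce; this is a check of the wording. First, the provisions side by side (all from the Protocol):

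| Step | Transaminases | Bilirubin or jaundice |
|---|---|---|
| Third interruption trigger (9.8.1) | ALT or AST >3× ULN | total bilirubin >2× ULN and/or jaundice |
| Follow-up after permanent discontinuation (9.8.1) | to normal or baseline | to normal or baseline, as applicable |
| Restart, any duration (9.8.1) | baseline or ≤2× ULN, whichever is higher | none stated |
| Restart after >72 hours (9.8) | general judgement | general judgement |
| Weekly tests after restart (9.8.1) | 4 weeks | 4 weeks |

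Bilirubin has a stated level at interruption and a stated endpoint after permanent discontinuation. It has neither at restart.

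Second, the rules applied to one child. The values are illustrative and do not come from the documents.

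1. *Interruption.* ALT 4× ULN, bilirubin 3× ULN. The first trigger needs ALT >8× (4 is not). The second needs >5× for more than 2 weeks (4 is not). The third needs ALT >3× with bilirubin >2× or jaundice (4 > 3 and 3 > 2, so it is met). With bilirubin at or below 2× ULN and no jaundice, ALT 4× would meet none of the three. Bilirubin is what made the interruption mandatory.
2. *Restart as written in 9.8.1.* Later, ALT and AST are at or below 1.9× ULN, bilirubin is 2.5× ULN, and a reversible cause has been identified. The test is transaminases ≤2× ULN or baseline; 1.9 ≤ 2, so it is met. Bilirubin of 2.5× ULN, or visible jaundice, is not tested.
3. *Section 9.8.* If the interruption lasted more than 72 hours, the investigator must also judge stability and added risk. If it lasted 72 hours or less, that condition does not apply by its terms. What remains in 9.8.1 is the identified cause and notice to the medical monitor.
4. *Restart with the proposed clause.* Bilirubin exceeded 2× ULN, so the clause is active. At 2.5× the child waits (unless baseline was that high). At ALT 1.9×, bilirubin 1.9× and no jaundice, the child may restart.
5. *A child outside the clause.* One interrupted at ALT 9× ULN, whose bilirubin never exceeded 2× and who was never jaundiced, restarts under exactly the present rule.

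**The case against.** The strongest reply is that the restart sentence is permissive and does not stand alone. It says drug may be resumed, and it sits under Section 9.8. A child who is still jaundiced is an obvious candidate for refusal on stability or added risk. Confirmatory testing alone is set at 48 to 72 hours, after which a cause must be found and transaminases must fall. Most liver interruptions would therefore probably exceed 72 hours, although this is inference, since the documents give no durations. Sections 9.7 (stopping for unacceptable toxicity) and 9.9 (withdrawal for safety) give further discretion. The central laboratory alerts the medical monitor to liver elevations, and a DMC reviews safety data.

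Much of this stands. A reader might infer that the protocol calls for, or freely allows, re-dosing of children who are still jaundiced. The documents do not support that, because Section 9.8 is equally part of the written rule. What does not go away is that Section 9.8 relies on opinion, names no liver value and does not reach shorter interruptions. The medical monitor is to be notified; approval is not required.

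A reader might also infer that restart contradicts the entry criteria, since total bilirubin of 2× ULN or more excludes a child at screening (Section 8.2, criterion 3). That does not follow, because the protocol does not use entry limits as its restart standard. ALT of exactly 2× ULN bars entry but allows restart. Every child who meets a liver interruption trigger has had ALT or AST above 3× ULN, which under criterion 10 would exclude from Part B had it occurred in the year before entry. The entry limit is a convenient source for a number and is not evidence of an inconsistency.

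Finally, whether bilirubin alone should ever trigger interruption is a separate question. This point neither depends on it nor changes it.

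**Conclusion.** The omission is real and narrow. Section 9.8.1 includes raised bilirubin and jaundice in the scope of its restart rule but sets a recovery condition only for transaminases, and neither document gives a bilirubin or jaundice limit for restart elsewhere. A child interrupted under the third trigger can meet the specific liver criterion while the sign that helped force the interruption persists. Beyond 72 hours the remaining protection is general clinical judgement; at 72 hours or less, that condition does not apply by its terms.

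The practical size is small. Few children are likely to be affected, the documents give no rate, and many clinicians would wait without being told to. No estimate, sample size or analysis changes. This is a cheap patient-safety improvement that should be made. It rests on reading the Section 9.8 stability condition as tied to interruptions over 72 hours, as that paragraph is framed. If it was meant for every interruption, the gap for shorter ones narrows to the absence of a stated bilirubin level.

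**What to change.** Amend the restart sentence in Protocol Section 9.8.1 so that resumption requires both of the following:

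- transaminases at baseline or ≤2× ULN, whichever is higher (unchanged);
- if total bilirubin exceeded 2× ULN or clinical jaundice was present at the trigger or at any time during the interruption, total bilirubin below 2× ULN (or at baseline, if that is higher) and jaundice resolved.

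Keep the existing requirements for an identified cause, notice to the medical monitor and weekly testing. The 2× ULN level already appears in the third interruption trigger and in exclusion criterion 3. Using it at restart is a clinical choice, and the sponsor may prefer a stricter value.

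The cost is one clause. Bilirubin is already followed as clinically indicated during a liver interruption and weekly for 4 weeks afterwards. The downside is a few slightly later restarts and perhaps an occasional extra bilirubin test. The SAP needs no change.

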9.8.2 Rash

Individuals who develop a generalized rash will be monitored closely. Study drug dosing should be interrupted if a subject develops a generalized rash of Grade 3 or higher (Section 13.1.1.4), or a rash that is considered a serious adverse event (SAE). The investigator will notify the medical monitor of any rash that results in interruption of study drug, is Grade 3 or higher (Section 13.1.1.4), or is an SAE. Investigators should consider additional evaluation including laboratory testing (e.g., complete blood count with differential, liver function tests), photographs of the rash, and dermatology consultation. The investigator may consider resumption of study drug if considered clinically appropriate.

9.9 Removal of Subjects

Subjects (or subjects' parent/legal guardian) may withdraw from the study at any time at their own request. Subjects may be withdrawn at any time at the discretion of the investigator or Vertex for safety, behavior, noncompliance (study drug dosing or study procedures), or administrative reasons. A subject who withdraws (or is withdrawn by parent/legal guardian) from study drug treatment will continue to be followed unless the subject (or parent/legal guardian) withdraws consent.

In addition, a subject must be discontinued from study drug treatment if the subject meets any of the following criteria:

- Has a screening *CFTR* genotype that does not confirm study eligibility if a previous *CFTR* genotype laboratory report was used to establish eligibility. These subjects must be discontinued from the study (Section 8.1)
- Meets any of the stopping (discontinuation) criteria (Section 9.8)

Subjects who discontinue study treatment early should continue to return for study assessments, as noted in Section 9.1.4.

If a subject does not return for a scheduled visit, reasonable effort will be made to contact the subject. In any circumstance, reasonable effort will be made to document subject outcome. The investigator will inquire about the reason for withdrawal, request that the subject return all unused investigational product(s), request that the subject return for a Safety Follow-up Visit, if applicable (see Section 9.1.4), and follow up with the subject regarding any unresolved AEs.

If a subject withdraws consent for the study, no further assessments will be performed. Vertex may retain and continue using the study data and samples after the study ends, and may use the samples and information in the development of the study compound, for other drugs and diagnostics, in publications and presentations, and for education purposes. If a subject withdraws from the study, the study data and samples collected will remain part of the study. A subject will not be able to request the withdrawal of his/her information from the study data. A subject may request destruction of the samples collected from him/her during the study as long as those samples can be identified as his/her samples.

9.10 Replacement of Subjects

Part A

Subjects who withdraw or are withdrawn for nonsafety reasons during the study drug Treatment Period may be replaced as needed in Part A, based on emerging PK data, to confirm the dose(s) for Part B.

Part B

Subjects who withdraw or are withdrawn for nonsafety reasons during the study drug Treatment Period may be replaced at Vertex's discretion.

10 STUDY DRUG INFORMATION AND MANAGEMENT

10.1 Preparation and Dispensing

Study drug may be dispensed only under the supervision of the investigator or an authorized designee and only for administration to the study subjects. An interactive web response system (IWRS) will be used to dispense dosage based on subject weight.

10.2 Packaging and Labeling

Study drug granules will be supplied in capsules in bottles in Part A and in sachets in Part B by Vertex. Study drug labeling will be in compliance with applicable local and national regulations. Additional details regarding packaging, labeling, and dispensing for study drug will be in the Pharmacy Manual.

10.3 Study Drug Supply, Storage, and Handling

Table 10-1 provides the study drug information. The investigator, or an authorized designee (e.g., a licensed pharmacist), will ensure that all investigational product is stored in a secured area, under recommended storage conditions, and in accordance with applicable regulatory requirements. To ensure adequate records, all study drugs will be accounted for as described in Section 10.4 or via the drug accountability forms as instructed by Vertex.

Detailed instructions regarding the storage, handling, and dispensation of the study drug will be provided in the Pharmacy Manual.

Table 10-1 Study Drug: Dosing Form/Route/Strength

Drug Name, Dosing Form, Route	Study Drug Strength		
	Part A: All Subjects	Part B: Subjects ≥ 10 kg to <14 kg at Day 1	Part B: Subjects ≥ 14 kg at Day 1
ELX/TEZ/IVA, FDC granules, oral			
ELX	100 mg	80 mg	100 mg
TEZ	50 mg	40 mg	50 mg
IVA	75 mg	60 mg	75 mg
IVA, granules, oral	75 mg	59.5 mg	75 mg

ELX: elexacaftor; FDC: fixed-dose combination; IVA: ivacaftor; TEZ: tezacaftor

10.4 Drug Accountability

The pharmacist or designated study site staff will maintain information about the dates and amounts of (1) study drug received; (2) study drug dispensed to the subjects; and (3) study drug returned by the subjects. Subjects will be instructed to return all used and unused materials associated with the study drug to the site. These materials will be retained at the site according to instructions provided by Vertex or its designee. The study monitor will review study drug records and inventory throughout the study.

If a site uses a site-specific drug accountability system and/or process, including processes associated with the destruction of returned materials, the process must be documented and approved by Vertex. The study monitor must review the drug accountability documentation on a regular basis. The study monitor will promptly communicate to Vertex any discrepancies he/she is unable to resolve with the site.

10.5 Disposal, Return, or Retention of Unused Drug

The study site staff or pharmacy personnel will retain all materials returned by the subjects until the study monitor has performed drug accountability. The investigator will ensure that the materials are destroyed in compliance with applicable environmental regulations, institutional policy, and any special instructions provided by Vertex. Destruction will be adequately documented.

The principal investigator, study site staff, including pharmacy personnel will assist Vertex with any recall activities (as applicable) and place impacted investigational medicinal product (IMP) in quarantine when requested.

